3.5 Adverse Events

Both the number of adverse events (AEs) and serious adverse events (SAEs) will be summarized by treatment group. The total number of (S)AEs, rate of (S)AEs per participant-month of follow-up, the average number of (S)AEs per participant, and the number of participants with at least one (S)AE will be provided. The number of (S)AEs per participant in each treatment group will be graphically represented as well as the proportion of participants in each treatment group experiencing at least one (S)AE by System Organ Class (SOC). Event counts and number of participants will be summarized for each SOC and (S)AE Preferred Term (PT) by treatment group, rates of (S)AEs by SOC will also be summarized. The number and percent of adverse events occurring will also be tabulated by severity.

The corresponding descriptive summaries and analyses are outlined in Appendix A, Section A.5 and a listing of serious adverse event narratives will be provided in Appendix B.

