11 ADVERSE EXPERIENCE REPORTING AND DOCUMENTATION

11.1 Adverse Events (AE)

An AE is any untoward medical occurrence in a clinical investigation of a patient administered a pharmaceutical product and that does not necessarily have a causal relationship with the treatment. An AE is therefore any unfavorable and unintended sign (including an abnormal laboratory finding), symptom or disease temporally associated with the administration of an investigational product, whether or not related to that investigational product. An unexpected AE is one of a type not identified in nature, severity, or frequency in the current Investigator's Brochure or of greater severity or frequency than expected based on the information in the Investigator's Brochure.

The Investigator will probe, via discussion with the subject, for the occurrence of AEs during each subject visit and record the information in the site's source documents. AEs will be recorded in the subject CRF.

AE Severity

The National Cancer Institute's Common Terminology Criteria for Adverse Events (CTCAE) Version 4.0, as modified for cystic fibrosis, should be used to assess and grade AE severity, including laboratory abnormalities judged to be clinically significant. The modified criteria can be found in the Study Reference Binder. If the experience is not covered in the modified criteria, the guidelines shown in Table 2 below should be used to grade severity. It should be pointed out that the term "severe" is a measure of intensity and that a severe AE is not necessarily serious.

Table 2. AE Severity Grading

Severity (Toxicity Grade)	Description
Mild (1)	Mild; asymptomatic or mild symptoms; clinical or diagnostic observations only; intervention not indicated
Moderate (2)	Moderate; minimal, local or noninvasive intervention indicated; limiting age-appropriate Instrumental activities of daily living (e.g., preparing meals, using the telephone, managing money)
Severe (3)	Severe or medically significant but not immediately life-threatening; hospitalization or prolongation of hospitalization indicated; disabling; limiting self-care activities of daily living (e.g., bathing, dressing, feeding self, using toilet, taking medications)
Life-threatening (4)	Life-threatening consequences; urgent intervention indicated
Death (5)	Death related to AE

AE Relationship to Study Drug

The relationship of an AE to the study drug should be assessed using the following the guidelines in Table 3.

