15.5 Analysis of Safety Endpoints

All reported treatment emergent SAEs and AEs will be coded using MedDRA and grouped by body system. Treatment emergent AEs are defined as AEs presenting post study treatment initiation. SAEs and AEs will be tabulated by treatment group using standard coding terms sorted by body system. The incidence of AEs in each treatment arm will be tabulated by severity.

The number of SAEs and AEs will be summarized for each treatment group as follows: (i) The proportion of subjects with at least one (S)AE, (ii) The average number of (S)AEs per patient, and (iii) The rate of (S)AEs per patient week of follow-up. Histograms showing the frequency of the number of (S)AEs in each treatment group will be included. Rates of (S)AEs by System Organ Class (SOC) will be presented by treatment group. Poisson regression modeling will be used to derive rate ratios and 95% CIs comparing overall S(AE) rates by treatment group as well as within each SOC. The rate ratios will be compared using a two-sided 0.05 level test for Poisson count data.

Safety lab data at Visit 2 and Visit 4 and changes from baseline will be summarized by treatment group. In addition, the following clinical laboratory summaries will be presented by treatment group: (i) the incidence of clinically significant abnormalities at each study visit; and (ii) tables summarizing the frequencies of subjects below, within, and above the normal reference ranges at baseline and end of study; and (iii) tables displaying baseline to end of study shifts in each laboratory value (shifts between below, within or above normal range).

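### SAP 3.5 describes adverse event severity by events only; the text plans no count of children by worst grade or with a severe event

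*SAP*

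**What the plan says.** SAP 3.5 on severity: "The number and percent of adverse events occurring will also be tabulated by severity". It does not state the denominator of the percentage.

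For other AE summaries the same section names participants explicitly. Overall, "the average number of (S)AEs per participant, and the number of participants with at least one (S)AE will be provided". By coding level, "Event counts and number of participants will be summarized for each SOC and (S)AE Preferred Term (PT) by treatment group".

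Protocol 15.5 on severity: "The incidence of AEs in each treatment arm will be tabulated by severity". It does not say whether incidence is counted in events or in subjects. Its participant-level summary, "The proportion of subjects with at least one (S)AE", is not split by grade.

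Protocol 11.1 separates severity from seriousness: the term severe "is a measure of intensity and that a severe AE is not necessarily serious".

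SAP 3.5 refers to its table outlines: "The corresponding descriptive summaries and analyses are outlined in Appendix A, Section A.5". Those outlines are not in the text available for this review.

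**The concern.** A safety reader wants to know how many children in each arm had a severe event. The child is the randomized unit, and events cluster within children. A table of events by grade cannot answer that question, because repeated severe events in one child and single severe events in several children produce the same row.

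The percentage has a second weakness. If its denominator is all events in the arm, that denominator is itself an outcome of treatment. An arm with more mild events then shows a smaller severe share, even when just as many children, or more, had a severe event.

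At stake is how clearly tolerability by grade can be read in a placebo-controlled paediatric phase II trial. The efficacy conclusion is not affected.

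**Working it through.** The documents state no severity figure, so there is nothing to reproduce. The check has two parts.

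**1. Unit of each AE summary in the text**

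| Summary | Source | Participants counted? | Split by severity? |
|---|---|---|---|
| At least one AE or SAE | SAP 3.5, Protocol 15.5 | Yes | No |
| By system organ class and preferred term | SAP 3.5 | Yes, with event counts | No |
| Severity | SAP 3.5 | No, events only | Yes |
| Severity | Protocol 15.5 | Unit not named | Yes |

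No row is clearly both participant-level and split by severity.

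**2. What an event-only entry can hide**

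Inputs: about 60 children with equal allocation (Protocol 15.9 and 8.1), so 60/2 = 30 per arm. All event counts below are assumptions, because the documents give none. The denominator of the planned percentage is taken as all events in the arm.

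- Event share = severe events / all events in the arm.
- Child share = children with at least one severe event / 30.

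Reference arm: 40 mild + 14 moderate + 6 severe = 60 events.

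*Clustering*
- Six severe events in six children: event share 6/60 = 10.0%; child share 6/30 = 20.0%.
- Six severe events in one child: event share 6/60 = 10.0%; child share 1/30 = 3.3%.
- The planned entry is 6 (10.0%) in both cases.

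*Dilution.* Keep six severe events in six children and add m mild events, so the event share is 6/(60 + m):

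| Extra mild events m | Event share | Child share |
|---|---|---|
| 0 | 10.0% | 20.0% |
| 15 | 6/75 = 8.0% | 20.0% |
| 30 | 6/90 = 6.7% | 20.0% |
| 60 | 6/120 = 5.0% | 20.0% |
| 90 | 6/150 = 4.0% | 20.0% |

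*Reversal.* Suppose the other arm has twice as many severe events, 12 in 12 children (12/30 = 40.0%). Its event share is 12/(66 + m). This falls below 10.0% only when 66 + m > 120, that is m > 54. At m = 60 it is 12/126 = 9.5%. The printed rows would then be 6 (10.0%) and 12 (9.5%): the percentages run the opposite way to the children affected, but the doubled count stands beside them.

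The clustering result holds for any denominator based on events. Dilution and reversal depend on the inferred denominator.

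**The case against.** The other side has real weight.

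- **The count is printed.** The table gives the number as well as the percentage of events, so a doubling of severe events would be seen. A reader might infer that the table will make the arm with more severe events look safer. That holds for one column only, and in the example needs more than 54 extra mild events on a base of 60. The count still does not show how many children are affected.
- **Departure from the protocol.** A reader might infer that the SAP replaced a participant measure with an event measure. Protocol 15.5 names no unit for incidence by severity, and elsewhere in that section it says subjects when it means subjects. The SAP may simply be making an ambiguous phrase specific.
- **Expected mild events.** A reader might infer that the protocol predicts extra mild gastrointestinal events on GSH. Protocol 2.1 says only that drug-related events are likely to be gastrointestinal; it does not predict an excess or a grade.
- **The named endpoint.** Incidence of AEs is a safety endpoint (Protocol 5.2), and it is already summarised per child overall, by system organ class and by preferred term. The gap is confined to severity.
- **SAE data.** Grade 3 in Table 2 of Protocol 11.1 includes events that call for hospital admission, so serious and severe events overlap. SAE participant counts and narratives, and the proportion hospitalized (SAP 3.6), cover part of the gap. They miss severe events that are not serious.
- **Appendix A.5.** A participant row by grade may exist there, so one cannot say that the planned table lacks it.

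What survives is that the text names no participant count by severity, and no other summary it describes fully supplies one.

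**Conclusion.** The point holds as a modest, inexpensive improvement to the safety reporting. As written, SAP 3.5 plans severity by events only, and neither SAP 3.5 nor Protocol 15.5 plans the number of children by worst grade or with a severe event.

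In the illustration, the same table entry is compatible with anything from 3.3% to 20.0% of children affected. On the natural reading of the denominator, the percentage can fall from 10.0% to 4.0% through mild events alone.

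These sizes rest on assumed event counts and 30 treated children per arm. The finding concerns the text of SAP 3.5 and is subject to what Appendix A.5 contains. The documents do not support a claim of protocol departure, of a bias towards GSH, or of a failure to report AE incidence per child.

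**What to change.** In SAP 3.5, and in Appendix A.5 if it is not already there:

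- Tabulate the number and percentage of treated participants by worst severity grade in each arm, with the safety population of SAP 2.3 as denominator.
- Include the proportion with at least one AE of grade 3 or higher. A difference between arms with the Newcombe-Wilson interval of SAP section 3 is optional.
- Keep event counts by grade as a supplement, and state the denominator of any event percentage.

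If Appendix A.5 already has the participant rows, only the sentence in 3.5 needs to be aligned with it.

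Grade is already recorded for each AE (Protocol 9.1.13), so no new data are needed. The cost is programming and validating one more descriptive table. Efficacy analyses, power and alpha are unaffected.

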3.6 Pulmonary Exacerbations, Hospitalizations, Antibiotic and Steroid Use

The number of events, rate per participant-month, and proportion of participants experiencing at least one event will be shown for pulmonary exacerbations (PEs) and hospitalizations. The distribution of number of PEs and hospitalization days will be summarized. Additionally, a listing of hospitalizations showing length of stay and indication will be included.

Proportions of participants initiating intravenous, inhaled, and oral antibiotics will be presented by treatment group along with summaries of the number of days of use (by route). The proportion of participants initiating steroids will be presented.

The corresponding summaries and analyses are outlined in Appendix A, Section A.6.

3.7 Safety Laboratory Parameters

The following hematology and serum chemistry measures will be summarized: white blood cells (WBC), red blood cells (RBC), hemoglobin, hematocrit, platelets, segmented neutrophils, band neutrophils, lymphocytes, monocytes, eosinophils, basophils, high-sensitivity C-reactive protein (hs-CRP), sodium, potassium, chloride, bicarbonate (Total CO₂), gamma-glutamyl transferase (GGT), aspartate aminotransferase (AST), alanine aminotransferase (ALT), urea nitrogen, and creatinine.

For each measure, the number and percentage of emergent low and emergent high (including clinically significant low/high) from baseline to Week 24 will be tabulated. Emergent high values will be displayed graphically.

The corresponding summaries and analyses are outlined in Appendix A, Section A.7.

3.8 Anthropometric Endpoints

In addition to the primary endpoint of weight-for-age z-score, the following anthropometric endpoints will be summarized: weight (kg), weight-for-age percentile, Body Mass Index (BMI, kg/m²), BMI-for-age z-score, BMI-for-age percentile, height (cm), height-for-age z-score, and height-for-age percentile. Height-for-age z-score, BMI percentile and z-score, and height and weight percentiles will be calculated using CDC reference equations.

For each of these endpoints, a linear mixed effects model analogous to the primary endpoint model will be used. Least squares mean changes at Week 24 and the estimated treatment differences with corresponding 95% confidence intervals and p-values will be presented.

In addition to the model based estimates, summary statistics will be tabulated by treatment group for each endpoint at baseline, Week 12, and Week 24. Both absolute and relative changes from baseline will be presented for Week 12 and Week 24. Treatment differences, corresponding 95% confidence intervals, and p-values will be provided for the Week 24 absolute and relative changes. Figures displaying mean values and mean changes from baseline by treatment group across visits will be provided for each anthropometric endpoint.

The corresponding summaries and analyses are outlined in Appendix A, Section A.8.

3.9 Spirometry Endpoints

For participants ≥ 4 years at the time of randomization and able to reproducibly perform spirometry, the following spirometry endpoints will be summarized: forced expiratory volume over one second (FEV₁, liters), FEV₁ percent of predicted, forced vital capacity (FVC, liters), FVC percent of predicted, forced expiratory flow between 25% and 75% of vital capacity (FEF_{25%-75%}, liters/second), and FEF_{25%-75%} percent of predicted. Percent of predicted values will be calculated using the Global Lung Initiative multi-ethnic reference equations for ages 3-95.

For each of these endpoints, a linear mixed model analogous to the primary endpoint model will be used. Least squares mean changes at Week 24 and the estimated treatment differences with corresponding 95% confidence intervals and p-values will be presented.

In addition to the model based estimates, summary statistics will be tabulated by treatment group for each endpoint at baseline, Week 12, and Week 24. Both absolute and relative changes from baseline will be presented for Week 12 and Week 24. Treatment differences, corresponding 95% confidence intervals, and p-values will be provided for the Week 24 absolute and relative changes. Figures displaying mean absolute changes and relative changes from baseline by treatment group across visits will be provided for each spirometry endpoint.

The corresponding summaries and analyses are outlined in Appendix A, Section A.9.

3.10 Cystic Fibrosis Gastrointestinal Parent Questionnaire

The Cystic Fibrosis Gastrointestinal Parent Questionnaire asks parents if their child has regularly experienced any of the following 14 symptoms in the past 3 months: loss of appetite; weight loss or difficulty gaining weight; early satiety (feeling too full too easily); reflux or heartburn; recurrent vomiting; difficulty swallowing, pain with swallowing, feeling as though things get stuck when swallowing; abdominal pain; diarrhea; constipation or pain with stooling; blood in stool; rectal prolapse; yellowing of the skin (jaundice) or yellowing of the eyes (scleral icterus); excessive unexplained itching; unusual bruising and bleeding. Possible answers include “None,” “Mild,” “Moderate,” and “Severe.”

Each symptom will be summarized separately, with number and percentage of participants experiencing the symptom as “None,” “Mild,” “Moderate,” and “Severe” presented by treatment group for each study visit. Changes in symptoms from baseline to Visit 3 (Week 12) and Visit 4 (Week 24) for each participant will be summarized as worsened, improved, or no change with number and percentage of participants tabulated.

The corresponding summaries and analyses are outlined in Appendix A, Section A.10.

3.11 Inflammatory Markers

The following laboratory measures of inflammation will be summarized: fecal calprotectin, neutrophil counts, platelet counts and high-sensitivity C-reactive protein.

Fecal calprotectin, which is measured at Visit 2, Visit 3, and Visit 4, will be modeled using a linear mixed model analogous to the primary endpoint model. Least squares mean changes at Week 24 and the estimated treatment difference with corresponding 95% confidence intervals and p-values will be presented.

Inflammatory markers measured only at Visit 2 and Visit 4 (neutrophil, platelets, and hs-CRP) will be analyzed using ANCOVA adjusted for randomization strata. Estimated mean changes at Visit 4 (Week 24) and treatment differences for each secondary endpoint will be presented as well as corresponding 95% confidence intervals and p-values.

In addition to the model based estimates, summary statistics will be tabulated by treatment group for the each endpoint at the applicable visits. Absolute changes from baseline will be presented for post-baseline visits. Treatment differences, corresponding 95% confidence intervals, and p-values will be provided for the Week 24 absolute changes. Box plots displaying marker values by treatment group for each visit will be included for each inflammatory marker.

The corresponding summaries and analyses are outlined in Appendix A, Section A.11.

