ALT = alanine transaminase; CI = confidence interval; CRP = C-reactive protein; GSH = glutathione; SD = standard deviation; WBC = white blood cell.

The impact of glutathione on gut inflammation measured as fecal calprotectin levels before and after the treatment period was also evaluated. Interestingly, there was improvement in fecal calprotectin in subjects treated with glutathione which was found to be statistically significant (difference from baseline in the glutathione group -52.0 µg/g vs. placebo 0.5 µg/g, p<0.0001), however, treatment groups were significantly different at baseline (glutathione group 113.2 µg/g vs. placebo 76.1 µg/g, p = 0.008). This is illustrated in the figures below.

[figure not shown]

FIGURE 5. Change over time in fecal calprotectin levels: (A) comparison means, (B) GSH treatment group patients, (C) placebo group patients. GSH= glutathione.

A gastrointestinal symptom index was used to evaluate improvement, worsening, or development of new gastrointestinal symptoms while subjects received study drug or placebo. In the subjects treated with glutathione, no subject worsened in any of the 11 subjective measures used in this symptom index. Furthermore, there was a trend toward improvement in several gastrointestinal symptoms such as abdominal pain, flatulence, lack of appetite and more than 2 bowel movements per day in the patients treated with glutathione.

Study 2: In an observational study, 13 patients with CF ages 1-27 years who were using GSH (either oral or inhaled) were followed for 5.5 months [5]. Data collected included FEV₁, BMI and weight percentile. Significant improvement over baseline was noted for

FEV₁ (average improvement of 5.8 percentage points); weight percentile (average improvement of 8.6 percentage points); and BMI percentile (average improvement of 1.22 percentage points).

Three subjects experienced adverse effects during the study with one case each of fever, chest tightness and diarrhea. All of these symptoms improved without intervention. There was an average decline in baseline ALT in patients receiving glutathione suggesting no significant hepatotoxic effects with the use of either oral or inhaled glutathione.

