8 STUDY TREATMENTS

8.1 Method of Assigning Subjects to Treatment Groups

Randomization will occur centrally using a web based randomization system linked to the electronic data capture (EDC) system. Eligible subjects will be randomly assigned to receive study drug (GSH or placebo) in equal allocation. Study personnel at the investigative site will

use the Medidata[®] Rave[®] and Balance[®] systems to randomize each subject. An adaptive randomization scheme (dynamic allocation based on minimization [29]) will be employed with the goal of ensuring equal representation in each study arm and strata. Subject randomization will be stratified by sex, baseline age (< 6 years, ≥ 6 years), baseline weight-for-age z-score (< -0.52, ≥ -0.52, i.e., the 30th percentile) and historical fecal elastase (<200 µg/g, ≥200 µg/g, unavailable). The dynamic allocation algorithm seeks to optimize randomization balance by minimizing a weighted average of the marginal imbalance [30] of treatment allocation for each factor and for the study overall. A random element is added to the otherwise deterministic minimization algorithm to reduce allocation predictability by using a biased coin (32) to include a chance of allocation to a treatment arm other than the arm that optimizes balance.

Only authorized site personnel are given access to the randomization module. Authorized site personnel will enter subject eligibility information and whether or not the subject signed informed consent. The system will verify that the subject is eligible and has provided signed informed consent; the system will then provide the appropriate authorized site personnel with a randomization assignment for the subject that matches a specific treatment.

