9.2.2 Blood Chemistry Profile

Blood will be obtained as noted in the Schedule of Events and sent to each site's clinical chemistry lab for determination of high-sensitivity C-reactive protein (hs-CRP), aspartate aminotransferase (AST/SGOT), alanine aminotransferase (ALT/SGPT), gamma-glutamyl transferase (GGT), and an electrolyte panel (sodium, potassium, chloride, bicarbonate) and renal function (BUN and creatinine). If values are abnormal and clinically significant (with an exception of hs-CRP) at Visit 4, a sample will be collected and these parameters re-evaluated at a follow-up visit two weeks later.

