15 STATISTICAL METHODS AND CONSIDERATIONS

15.1 General Considerations

Prior to the analysis of the final study data, a detailed Statistical Analysis Plan (SAP) will be written, describing all analyses that will be performed. The SAP will contain any modifications to the analysis plan described below. All analyses will be performed using SAS® (SAS Institute, Inc., Cary, NC, USA) or R (R Foundation for Statistical Computing, Vienna, Austria).

For the purposes of analyses, baseline will be defined as Day 0 (Randomization/Visit 2). Except where otherwise noted, comparisons of continuous variables between treatment arms will utilize two-sample t-tests or multiple linear regression/ANOVA, proportions will be compared using Fisher's exact test, and rate ratios will be compared using Poisson regression. Except where otherwise noted, all tests will be two-sided and statistical significance will be determined at the 0.05 level. Missing data methods for the primary and key secondary endpoints will be described in the SAP. No adjustment for multiple comparisons will be made.

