15.9 Sample Size

The primary endpoint is the difference between treatment groups of the change in weight-for-age z-score from Visit 2 to Visit 4 (Week 24). Data from prior studies of similar populations and durations are available to estimate sample size and power for the study including a randomized, placebo-controlled trial of oral GSH in Italian children chronically taking pancreatic enzymes, as well as a factorial randomized trial comparing antipseudomonal regimens in US children with newly acquired *Pseudomonas aeruginosa* infection. These studies suggest a standard deviation of the change in weight-for-age z-score ranging from 0.20 to 0.29. A query of CF registry data of a similar population found the standard deviation of the 6-month change in weight-for-age z-score to be higher (0.37). A previous study of oral GSH in children, conducted in Italy, found the weight-for-age z-score difference between the GSH arm and the placebo arm after 6 months of therapy to be 0.34. The following table provides example weight changes in kilograms over a 6 month period for certain patient age and sex combinations, as well as how those gains translate into changes in weight-for-age z-score.

Subject Age and Sex at Baseline	Weight Baseline (kg)	Weight Visit 4 (kg)	6-month change (kg)	Weight at baseline (z-score)	Weight at Visit 4 (z-score)	6 month change (z-score)
9-year old boy	25	28	3	-0.87	-0.46	0.42
7-year old girl	19	20.75	1.75	-1.27	-1	0.27
3-year old boy	14	15.25	1.25	-0.21	0.01	0.22
4-year old girl	15	17.5	2.5	-0.4	0.28	0.68

The figure below displays a range of detectable treatment effect sizes and resulting sample sizes for 3 standard deviations (SD = 0.2, 0.3 and 0.4) Assuming a conservative standard deviation of 0.4, a total sample size of 54 provides 90% power to detect a treatment effect of 0.36 or greater. It is anticipated from prior CF trials conducted through the TDNCC that the attrition rate will be less than 10% for a study of this duration, thus it is reasonable to expect that a total sample size of 60 will enable at least 54 subjects to complete the trial.

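### SAP 3.11 names neither a log scale nor a baseline-marker covariate for fecal calprotectin and hs-CRP; if these markers are right-skewed with proportional effects, power can be lost and the estimate depends on the starting level

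*SAP*

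**What the plan says.** SAP 3.11 covers four inflammatory markers. Fecal calprotectin, measured at Visits 2, 3 and 4, "will be modeled using a linear mixed model analogous to the primary endpoint model". That primary model (SAP 3.4) is a linear mixed model for weight-for-age z-score, adjusted for sex, age group, baseline weight z-score category and historical fecal elastase. Neutrophils, platelets and hs-CRP, measured at Visits 2 and 4 only, get an ANCOVA; the randomization strata are the only adjustment named. For the descriptive comparison, "Absolute changes from baseline will be presented for post-baseline visits". SAP 3.8 and 3.9 keep both absolute and relative change for anthropometry and spirometry.

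Protocol 15.4 differs in two ways. It puts calprotectin in the list of endpoints analysed as absolute and relative changes, and it names ANOVA for the Visit 2 and Visit 4 markers. Protocol 15.1 lets the SAP modify the plan, but the SAP gives no reason for either change.

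Neither document mentions a log scale, a ratio of geometric means, a rank-based method, a residual check or a rule for values below a reporting limit for these markers. The only logarithm in the SAP is the Poisson offset.

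**The concern.** Calprotectin and hs-CRP are concentrations that cannot fall below zero. Such measures are often right-skewed, with treatment effects closer to proportional than additive. If that is so here, a few high values dominate the mean change and its standard error, and one proportional effect gives a different µg/g difference at each starting level.

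The starting level matters in this trial. Protocol 1.2 reports that the earlier trial's arms differed in baseline calprotectin, 113.2 against 76.1 µg/g (p = 0.008). Protocol section 2 gives that imbalance as a reason why the earlier result is not conclusive, and promises better balance through stratification. Yet the factors in Protocol 8.1 are sex, age, weight z-score and historical fecal elastase. Calprotectin is not among them, and SAP 3.11 names no baseline-marker covariate. The weakness the protocol criticises could therefore recur by chance, with nothing in the written model to absorb it.

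What is at stake is a secondary endpoint: a real fall in intestinal inflammation could be missed, or its size misjudged.

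**Working it through.** **The plan's own figure.** Protocol 15.9 says: "Assuming a conservative standard deviation of 0.4", "a total sample size of 54 provides 90% power to detect a treatment effect of 0.36 or greater". With 27 per arm (allocation is equal, Protocol 8.1), the noncentrality is 0.36 / (0.4 × √(2/27)) = 3.31. A two-sided 0.05 t-test on 52 df then has 90.1% power, so the figure reproduces. It covers the primary endpoint only; no power is stated for any marker.

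**Spread implied by the documents.** No SD, skewness or correlation is given for calprotectin. The baseline p-value allows an estimate if the 44 children were split 22 and 22 and the test was a t-test (both assumed).
- t for p = 0.008 on 42 df is 2.785.
- SD = (113.2 − 76.1) / (2.785 × √(2/22)) = 44.2.
- Mean = (113.2 + 76.1)/2 = 94.65, so CV = 0.467.
- If log-normal, log-SD = √ln(1 + 0.467²) = 0.44.

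As a check on the arm sizes, the earlier trial's CRP changes of −2.6 (SD 3.1) and 2.6 (SD 2.9) with 22 per arm give a 95% CI of −7.03 to −3.37, matching the printed −7.0 to −3.4. Splits of 21/23 and 24/20 round to the same interval, so this supports the assumption without proving it.

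**Effect.** The protocol gives "difference from baseline in the glutathione group -52.0" µg/g. 52.0/113.2 = 45.9%, a ratio of 0.541, with ln(0.541) = −0.615.

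**Power for calprotectin.** Assumptions: log-normal marker, proportional effect, 27 per arm, log-scale correlation 0.5, two-sided 0.05, complete data. Under complete data and an unstructured covariance with no baseline constraint, the mixed model's Week 24 contrast is essentially a comparison of change scores. For log change, the SD of the change is s × √(2(1 − 0.5)) = s, so the noncentrality is 0.615 / (s × √(2/27)). Raw change has no simple formula and was simulated.

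| Log-SD s | Raw change (simulated) | Log change (simulated) | Log change (noncentrality; power) |
|---|---|---|---|
| 0.45 | 96% | 99.9% | 5.02; 99.8% |
| 0.6 | 78% | 96% | 3.77; 96% |
| 0.8 | 48% | 80% | 2.82; 79% |
| 1.0 | 28% | 61% | 2.26; 60% |

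Repeat simulations move these by one or two points. With no effect, raw change rejects in 5.2% of trials at log-SD 0.45 and 4.1% at 1.0, so Type I error is not inflated.

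For a smaller effect, set so that log change has 80% power, raw change at log-SD 0.45 has about 65%.

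**With the baseline marker as covariate.** At correlation 0.5 and a ratio of 0.537 (0.541 over the placebo ratio 1.007), ANCOVA power raw against log is 76% against 89% at log-SD 0.8, and 50% against 73% at 1.0. At log-SD 0.8 the covariate alone takes the raw analysis from 48% to 76%, and the log scale adds the rest. At log-SD 0.45, for the effect set to give log change 80%, the raw-to-log gap with the covariate is 3 to 6 points over correlations 0.3 to 0.7.

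**Dependence on starting level.** A 45.9% fall is 52.0 µg/g from 113.2, but 0.459 × 76.1 = 35.0 µg/g from 76.1.

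**Regression to the mean.** Log change does not remove it. If the 113.2/76.1 gap were chance and the correlation 0.5, log change under no effect would show an expected ratio of (113.2/76.1)^(0.5 − 1) = 0.82, an apparent 18% fall. Only adjusting for the baseline marker deals with this.

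**The case against.** The strongest reply is that the loss is assumed rather than shown. Log-normality, the proportional effect, the correlation and every log-SD above 0.45 come from outside the documents. At the one spread that can be recovered from them, and for the earlier trial's effect, raw change has 96% power and almost nothing is lost. If the effect is additive, the raw scale is not wrong. This stands: a reader might infer that the plan loses much of its power, and the documents do not support that.

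Other strong readings fail too.
- **hs-CRP.** A reader might carry the power figures over to it. They are for calprotectin only. The documents give no log-scale figure for hs-CRP, and the earlier trial's raw CRP changes separated the arms clearly.
- **A 17 µg/g artefact.** A reader might subtract 35 from 52 and call the result a spurious difference between arms. That needs both arms to fall by 46%; in the earlier trial placebo changed by +0.5.
- **Main test of mechanism.** Protocol 3.3 assigns mechanism to the exploratory redox and metabolite measures. Protocol section 2 does mention intestinal inflammation in that context, but calprotectin is one of many secondary endpoints.

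It can also be said that silence on transformation is not a decision to use the raw scale, that ANCOVA usually implies a baseline covariate, and that SAP 3.11 refers to Appendix A.11, which is not in the text reviewed. These points soften the criticism. Still, raw change adjusted for strata is the natural reading of SAP 3.11. A single-centre trial is also weak evidence that the spread will be as small across approximately 17 sites.

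**Conclusion.** The point holds in conditional form. SAP 3.11 names neither the log scale nor the baseline marker for calprotectin and hs-CRP, and lists only absolute changes where Protocol 15.4 also has relative change for calprotectin. If the markers are right-skewed with proportional effects, the raw analysis can lose power for calprotectin: about 4 points for a 46% fall at the spread implied by the earlier trial, 18 at log-SD 0.6, 32 at 0.8 and 33 at 1.0. These rest on 27 per arm and correlation 0.5; the 0.45 spread also assumes 22 per arm and a t-test in the earlier trial.

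Dependence on starting level is the firmer half, because the protocol itself faults the earlier trial for baseline imbalance and then does not stratify on calprotectin. Moving to log change without the baseline covariate would leave that half unsolved. The primary endpoint and sample size are untouched. Confidence in the size of the gain is moderate.

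**What to change.** Before unblinding, amend SAP 3.11 as follows.

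- Analyse calprotectin and hs-CRP on the log scale, with the log baseline value as covariate plus the randomization strata. For calprotectin, a mixed model with baseline means constrained equal across arms is an alternative.
- Report the Week 24 ratio of geometric means (GSH/placebo) with its 95% CI.
- State a rule for values below the reporting limit: treat them as left-censored, or set them to half the limit with one sensitivity check. This matters most for hs-CRP, which Protocol 9.2.2 sends to each site's own laboratory, so limits may differ.
- Keep the raw summaries and box plots as description.
- Reconcile SAP 3.11 with Protocol 15.4 on relative change for calprotectin and on ANOVA versus ANCOVA, with a reason for whichever is kept.

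The cost is SAP wording; no new data are needed. The small downside is that effects are stated as ratios rather than in µg/g or mg/L. Fixing the scale in advance also avoids any suspicion that it was chosen from the results.
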